6.5 Outcomes

6.5.1 Primary outcomes

Primary maternal outcome: Percentage time spent with maternal glucose levels within the pregnancy target range, as recorded by CGM Time-In-Range (TIR 3.5-7.8 mmol/L) across both arms from 20 until 38 weeks' gestation, or until delivery, if delivery is earlier than 38 weeks' gestation.

Primary neonatal outcome: NICU admission or death (stillbirth/neonatal death) across both arms.

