Study Type	An open-label, interventional, multicentre, randomised, single-period, two-arm parallel group trial with Stage 1 (internal pilot) to test the feasibility of recruitment and randomisation followed by the Stage 2 (substantive study) if the progression criteria are met.
Target Sample Size	422 (211 per arm)
Primary Outcomes	Primary maternal outcome:The percentage time spent with maternal glucose levels within target range, as recorded by CGM Time-In-Range (TIR 3.5-7.8 mmol/L) across both arms from 20 until 38 weeks' gestation or until delivery, if delivery is earlier than 38 weeks' gestation.Primary neonatal outcome:
	Neonatal unit admission or death (stillbirth/neonatal death).
Secondary Outcomes	 Biomedical maternal: 1. HbA1c & CGM mean glucose, GMI, frequency & duration of glycaemic excursions [%Time-Above-Range (>6.7 & >7.8 mmol/L), %Time-Below-Range (<3.5 & <3.0 mmol/L)], glycaemic variability (glucose SD, CV)] 2. Hypertensive disorders 3. Gestational weight gain

4	. Diabetes treatment (metformin & insulin use)
5	. Hospital admissions & duration of stay
6	. Severe hypoglycaemia, hyperosmolar hyperglycaemic state, and
	diabetic ketoacidosis episodes
	nedical neonatal:
	. Gestational age at birth
2	. Birth weight for gestational age (SDS) (GROW customised birth
	weight, LGA birth weight >90 th centile or SGA <10 th centile)
	. Mode of delivery
4	 Neonatal unit admission >24 hours (duration of stay, highest level care)
5	. Adverse events (pregnancy loss <24 weeks, congenital anomaly
	(any), stillbirth, neonatal death)
6	. Birth injury (spinal cord injury, clavicular, skull or bone fracture,
	shoulder dystocia, nerve palsy, subdural or intracerebral
	haemorrhage, hypoxic ischaemic encephalopathy)
7	. Neonatal morbidity (treatment for neonatal hypoglycaemia,
	respiratory distress requiring treatment, neonatal jaundice
	requiring treatment)
8	. Feeding at hospital discharge (exclusive breast-feeding / partial
	breast-feeding / exclusive formula feeding)
	breast-recuring / exclusive formula recuring)
Patie	ent Reported Outcomes:
1	. Diabetes distress, anxiety & depression and treatment satisfaction
	using short questionnaires at baseline & 32 weeks' gestation
2	. Nested qualitative study to explore the acceptability, barriers, and
	facilitators for CGM use in T2D pregnancy.
	th Economic Outcomes:
1	. Incremental cost per quality-adjusted life year (QALY)

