on their mobile phones. They find glucose TIR information engaging because it provides immediate feedback on any changes they make to their diet or diabetes treatments (19, 20)⁻(21). The patient-centredness of TIR is strongly endorsed by a survey of 3,461 people with diabetes (70% with T2D) who ranked TIR as the factor, which after food choices, has the biggest impact on their daily lives. In contrast to SMBG, CGM data are easily shared remotely with the users, carers and health care professional (HCP) teams allowing diabetes treatment plans (diet, metformin, insulin) to be more precisely adjusted (22-25). This is especially relevant during pregnancy where there are frequent changes in gestational physiology and pharmacokinetics requiring timely personalized treatment adjustments (26, 27).

We performed an international randomised controlled trial (RCT) of CGM use in T1D pregnancy (CONCEPTT)(28). We demonstrated that compared to finger-prick SMBG, CGM use was associated with improved maternal glucose levels with higher CGM Time In Range (TIR) during the third trimester. It was changes in CGM TIR (68% vs 61%; p=0·0034) and neonatal health outcomes [large for gestational age (LGA) birthweight odds ratio 0·51, 95% CI 0·28 to 0·90; p=0·0210, neonatal unit admission >24h odds ratio 0·48; CI 0·26 to 0·86; p=0·0157, neonatal hypoglycaemia 0·45; CI 0·22 to 0·89; p=0·0250), 1-day shorter neonatal hospital stay (p=0·0091)] that led to changes in NICE guidelines and accelerated NHS implementation (Dec 2020)(29). Providing CGM in T1D pregnancy dominated management with finger-prick SMBG, by being less expensive and more effective(14, 15). For maternal outcomes, CGM use was clinically and cost effective. For neonatal outcomes, CGM cost less (-£2,612) while being more effective (QALYs 75.4 vs. 73.8) making it cost-saving with an incremental cost-effective ratio (ICER) of *minus* £1,571/QALY gained. This was driven, almost exclusively, by fewer neonatal admissions (14).

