5.2 Objectives

Our main objective is to examine whether the use of CGM relative to standard care is clinically effective, cost effective and acceptable to pregnant women with EOT2D. Specific objectives are to:

- Test the primary hypothesis that in pregnant women with EOT2D the use of real-time CGM is more effective than standard clinical care (finger-prick SMBG testing) for improving the percentage of time spent in the pregnancy target glucose range of 3.5-7.8 mmol/L and reducing clinically relevant neonatal morbidity (neonatal care admission) or perinatal death.
- Estimate the incremental use of healthcare resources, costs and impact on health-related quality of life (measured using EQ-5D-5L questionnaire) associated with CGM relative to standard care.
- 3) Assess maternal acceptability of CGM use on diabetes treatment satisfaction, health-related quality of life and maternal wellbeing outcomes using qualitative interviews and validated questionnaires.
- 4) Examine the associations between maternal glycaemia (HbA1c and CGM Time-In-Range (TIR) metrics) with obstetric and neonatal health outcomes in EOT2D pregnancy.
- 5) Assess the proportion of women with EOT2D who give consent to be contacted for future studies.

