Infant data: High level neonatal care >24 hours, length of NICU stay, neonatal hypoglycaemia treated with buccal mucosa 40% glucose gel and/or iv dextrose, neonatal hyperbilirubinemia, respiratory distress, length of hospital stay.

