6.6.1.10 Neonatal follow up

Neonatal assessment is at hospital discharge (or 28 days if admission prolonged). The following data will be collected:

- Neonatal morbidity (treatment for neonatal hypoglycaemia, neonatal jaundice, respiratory distress)
- Neonatal care admission (duration of stay at each level of care: Level 3 intensive care, Level 2 high-dependency care, or Level 1 special care, recorded according to national guidance (BAPM 2010))
- Infant(s) feeding at hospital discharge (exclusive breast feeding/partial breast feeding/exclusive formula feeding)
- Neonatal readmission in the first 7 days after birth (e.g., for neonatal hyperbilirubinemia see section 9, outcome definitions)

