6.6.1.11 Early pregnancy loss

In the event of early pregnancy loss, trial follow-up will end (with the exception of follow up of any CGM- or study-related SAEs). Participants on the intervention arm may be asked to return unused devices to the research team.

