6.10.4 Statistical methods

6.10.4.1 Primary outcome analysis

Maternal glucose:

The primary analysis will evaluate the change in the time spent in the target glucose range (CGM TIR 3.5-7.8 mmol/L) between the intervention and control arm between 20 weeks' gestation and 38 weeks or until delivery (if delivered earlier), based on 4 x 14-day CGM assessments, at 20-22, 28-30, 32-34 and 36-38 weeks. The median gestation of delivery in T2D pregnancy is 38 weeks. A linear mixed effects regression model will be fit with CGM TIR from 20 weeks' gestation until delivery as the dependent variable adjusting for baseline CGM TIR, and subject as random effects. A point estimate, 95% confidence interval and p-value will be reported for the treatment effect based on the linear regression model. Residual values will be examined for an approximate normal distribution. If values are highly skewed, then a transformation or robust statistical methods will be used instead.

Neonatal outcomes:

The primary neonatal outcome is a composite of neonatal unit admission or death in line with section 6.10.4.3.

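### The primary neonatal outcome is worded inconsistently across the protocol, and no version carries the >24 h criterion attached to the odds ratio of 0.48 used for the sample size.

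*Protocol*

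**What the plan says.** Four sections state the primary neonatal outcome or the hypothesis about it:

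- **6.5.1 Primary outcomes:** "Primary neonatal outcome: NICU admission or death (stillbirth/neonatal death) across both arms".
- **2.3 Structured trial summary:** "Neonatal unit admission or death (stillbirth/neonatal death".
- **6.10.4.1 Primary outcome analysis:** "The primary neonatal outcome is a composite of neonatal unit admission or death in line with section 6.10.4.3".
- **5.2 Objectives:** "reducing clinically relevant neonatal morbidity (neonatal care admission) or perinatal death".

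None gives a minimum length of stay or names the levels of care that qualify. Section 6.10.4.3, to which 6.10.4.1 refers, sets out the method for dichotomous outcomes, but its list includes neither neonatal admission nor the composite.

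The 24-hour threshold appears elsewhere. Section 5.1 uses it to describe serious neonatal morbidity in the national audit, and reports the earlier type 1 diabetes trial as "neonatal unit admission >24h odds ratio 0·48". In 2.3 it belongs to a secondary outcome, and the matching item in 6.5.2 omits it. The infant data note to the timeline in 6.6 lists "High level neonatal care >24 hours, length of NICU stay".

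Section 6.7 takes 42.2% from the audit and 0.48 from the earlier trial, calls the event neonatal care or neonatal unit admission without a duration, and adds that it involves separating the newborn from the mother.

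**The concern.** This outcome sets the size of the trial. Intensive care admission, admission to any neonatal unit, and admission beyond 24 hours are different events, with different frequencies and possibly different treatment effects. If the odds ratio was observed on one event and the trial counts another, the stated 90% power does not describe the analysis that will be done.

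The trial is also open-label (6.8.2), and the decision to admit a baby briefly for observation is partly discretionary. The threshold that separates short from longer stays should therefore be settled in the protocol and not left to interpretation.

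**Working it through.** **1. Reproduce the plan's figure.** Inputs from 6.7: 42.2% against 26.0%, two-sided 5%, 90% power, 10% drop-out. Allocation is 1:1 (6.8.1.1).

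- Odds ratio: (0.260/0.740) / (0.422/0.578) = 0.481, as stated.
- Uncorrected size per arm, with mean proportion 0.341 and difference 0.162: n = [1.960 × √(2 × 0.341 × 0.659) + 1.282 × √(0.422 × 0.578 + 0.260 × 0.740)]² / 0.162² = 177.9.
- Continuity correction: n′ = (n/4) × [1 + √(1 + 4/(n × 0.162))]² = 190.0.
- Drop-out: 2 × 190 / 0.9 = 422. This matches. Without the correction, rounding up to 178 per arm gives 356/0.9 = 396, so the plan used the correction.
- Composite, 48.8% against 31.7%, by the same route: 183 per arm, 366/0.9 = 407, against 406 stated. This agrees within rounding.

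The arithmetic stands. The question is what event the inputs measure.

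**2. Trace each input to its event.**

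| Item | Where | Event described |
|---|---|---|
| Odds ratio 0.48, as a result | 5.1 | Neonatal unit admission >24 h |
| Odds ratio 0.48, as an assumption | 6.7 | Neonatal unit admission, no duration |
| Control rate 42.2% | 5.1 and 6.7 | Neonatal morbidity; neonatal care outcome. Probably >24 h, because 5.1 describes serious neonatal morbidity that way, but this is not stated outright |
| Primary outcome | 6.5.1 | NICU admission, no duration |
| Primary outcome | 2.3 and 6.10.4.1 | Neonatal unit admission, no duration |
| Hypothesis | 5.2 | Neonatal care admission, no duration |

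The effect size carries a criterion that no statement of the primary outcome carries.

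**3. Would a literal reading of 6.5.1 matter?** Section 6.6.1.10 records stay separately for intensive, high-dependency and special care, and section 9 describes these and transitional care as distinct categories. Neither says which count. Intensive care alone is a subset of neonatal unit admission and so is rarer.

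**4. Sensitivity, for illustration only.** The protocol gives no rate for intensive care alone or for admission of any length, so the rates here are assumptions. All use 190 analysable women per arm and the same corrected formula.

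- *Narrower event.* Assume intensive care admission in 10%, 15%, 20% or 25% of controls and keep the odds ratio at 0.48. Power is 37%, 53%, 66% or 75%. These figures leave out deaths. Adding the 6.7% in 5.1 without overlap turns 10% and 20% into 16.7% and 26.7%, with power of 58% and 78%.
- *Broader event.* Start from the composite, 48.8% against 31.7% (power 91%). Assume short stays add an event in 5%, 10% or 15% of otherwise event-free infants in both arms. The difference, 17.1 × (1 − share added), becomes 16.2, 15.4 or 14.5 points, and power 87%, 83% or 78%.

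These show that the choice of event matters. They do not measure a shortfall.

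**5. Death window.** Section 6.10.4.3 counts neonatal death to 28 days. Section 6.6.1.10 says "Neonatal assessment is at hospital discharge (or 28 days if admission prolonged", and adds readmission in the first 7 days. For an infant discharged early, no listed procedure establishes survival to day 28.

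**The case against.** The best defence is that NICU in 6.5.1 is loose wording. Every other statement of the outcome says neonatal unit or neonatal care, 6.6.6.3 uses NICU loosely for babies at another centre, and section 9 calls its top tier intensive care. This is probably right. It removes the intensive-care reading as a likely intention, but the controlling outcome section still contradicts the others and has to be corrected.

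A second defence is that the missing duration may be deliberate, since 2.3 lists a primary outcome without >24 h beside a secondary outcome with it. That is possible, and >24 h is indeed nowhere written as a rival primary definition. But if any duration is intended, 0.48 was borrowed from a different event and 6.7 does not say so.

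Third, the protocol is not silent on transitional care. The separation wording in 6.7 implies exclusion, since section 9 has the mother resident with her baby there, and 6.6.1.10 records only the three higher levels. That stands. Approval of the SAP before database lock (6.10.4.7) also limits the scope for a choice driven by the data, though it does not remove the contradiction.

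Two stronger readings are tempting and not supported:

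- *The trial is underpowered.* This would need event rates that the protocol does not contain. Powering on admission alone while analysing the composite is disclosed and is no fault, as the composite needs fewer women.
- *Early losses would be scored as free of events.* Section 6.6.1.11 says "In the event of early pregnancy loss, trial follow-up will end", but nowhere does the protocol say how such women enter the primary analysis. Loss before 24 weeks is a separate listed outcome, and the denominator rule is commonly left to the SAP.

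**Conclusion.** The point holds as an internal inconsistency in the outcome that sets the sample size. Section 6.5.1 conflicts with 2.3, 5.2 and 6.10.4.1 on the kind of admission, and no version has the >24 h criterion under which 0.48 was reported. The event analysed therefore need not be the event powered.

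The calculation itself is correct for its inputs, and the size of any power loss cannot be fixed from the protocol. That 42.2% also refers to stays over 24 hours is a reasonable inference from 5.1 and not an explicit statement. The mismatch between the 28-day death window and follow-up is real but minor. The inconsistency should be resolved before analysis because it concerns a primary outcome, and it is cheap to resolve.

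**What to change.** 1. Replace NICU admission in 6.5.1, and use one definition in 2.3, 5.2, 6.5.1, 6.7, 6.10.4.1 and section 9. State the qualifying levels of care, whether transitional care is excluded (as 6.7 implies), the minimum duration, and one term for the deaths counted.
2. Confirm that 42.2% and 0.48 refer to that event. Either align the primary outcome to admission >24 h, the basis of the effect size, with admission of any duration as a sensitivity analysis; or keep any duration and restate the power assumption in 6.7 for that event.
3. Make the secondary admission item agree between 2.3 and 6.5.2, and the infant data note in 6.6 agree with 6.6.1.10.
4. Reconcile the 28-day death window with neonatal follow-up, for example by a records check of status at day 28.

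**Cost.** Level and duration of care are already collected under 6.6.1.10, so no new admission data are needed. The work is one derivation rule, a small records task, and a protocol amendment submitted for approval under 8.4, since the wording of a primary outcome changes.

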6.5.2 Secondary outcomes

Biomedical maternal:

- HbA1c and CGM mean glucose, glucose management indicator (GMI), frequency and duration of glycaemic excursions [%Time-Above-Range (>6.7 & >7.8 mmol/L), %Time-Below-Range (<3.5 & <3.0 mmol/L)], glycaemic variability (glucose SD, CV)]
- 2) Hypertensive disorders
- 3) Gestational weight gain (from initial antenatal visit to 36 weeks' gestation)
- 4) Diabetes treatment (metformin and insulin use)
- 5) Hospital admissions and duration of stay
- 6) Severe hypoglycaemia, hyperosmolar hyperglycaemic state, and diabetic ketoacidosis episodes

Biomedical neonatal:

- 1) Gestational age at birth
- 2) Mode of delivery
- Birth weight for gestational age (SDS) (GROW customised birth weight, LGA birth weight >90th centile or SGA <10th centile)
- 4) Neonatal care unit admission (duration of stay, highest level care)
- 5) Adverse events (pregnancy loss <24 weeks, congenital anomaly (any), stillbirth, neonatal death)
- 6) Birth injury (spinal cord injury, clavicular, skull or long bone fracture, shoulder dystocia, nerve palsy, subdural or intracerebral haemorrhage confirmed by computerized tomography (CT) or magnetic resonance imaging (MRI) scan, hypoxic ischaemic encephalopathy)
- 7) Neonatal morbidity (treatment for neonatal hypoglycaemia; treatment for respiratory distress; treatment for neonatal jaundice)
- 8) Feeding at hospital discharge (exclusive breast-feeding / partial breast-feeding / exclusive formula feeding)

Patient-reported outcome measures (PROMs):

Diabetes distress, anxiety and depression and treatment satisfaction using short questionnaires at baseline (except for GMSS which is applicable only in late pregnancy) and 32 weeks' gestation:

- T2D Distress Scale (DDS)
- Glucose Monitoring Satisfaction Survey (GMSS)
- Patient Health Questionnaire 9-item depression scale (PHQ-9)
- Generalized Anxiety Disorder 7-item scale (GAD-7)
- EQ-5D-5L (maternal)

The nested qualitative study will also explore the acceptability, barriers, facilitators as well as patient and HCP support needs for CGM use in T2D pregnancy.

6.5.5 Health economic outcomes

A within-trial cost utility analysis comparing Freestyle Libre 3 CGM with standard care under the intention-to-treat principle. An NHS and personal social care perspective and a societal perspective will be adopted. The primary outcome measure of the health economics analysis will be incremental cost per quality-adjusted life year (QALY). The health-related quality of life instrument EQ-5D-5L collected at baseline and 32 weeks will provide maternal utility values for the calculation of QALYs.

6.6 Participant timeline

	Initial Contact	Recruitment visit	Randomis- ation visit	Routine antenatal appts	28-week visit	32-week visit	36-week visit	Delivery visit	Hospital discharge (infant)
	Early pregnancy	≥4 days prior to randomisation	≤16+0 weeks' gestation	16, 20 & 24 weeks' gestation	(+/- 2 weeks)	(+/- 2 weeks)	(+/- 2 weeks)		
Patient information provided (hard copy and/or electronic)	х								
Check inclusion / exclusion criteria		Х							
Obtain written informed consent		Х							
Height and weight, medical history		Х							
HbA1c (local lab)		X ⁺			х	х	Х		
Bloods for metabolic phenotyping		х	^						
Masked CGM sensor		Х		X* (week 20 only)	X*	X*	X*		
Questionnaires		Х	confirm completed			Х			
Adverse event collection		Adverse	Events of Special	Interest (AESI) & S	Serious Adverse E	vents (SAEs) repo	rted in line with se	ection 7	
Randomisation			Х						
CGM (Intervention arm only)**			Real-time CG	M data uploaded	l via smartphone o	or receiver from r	andomisation to p	ost-delivery	
Qualitative interviews (selected interve	ention particip	ants)			Scheduled	between researc	her and participar	nt during or after	pregnancy
! Trial data collection				х	х	х	х		
!! Data collection at delivery								Х	
# Infant care and feeding data									х

[†]Only required if not previously performed in this pregnancy

^ Bloods for metabolic phenotyping to be taken at baseline, after written informed consent, or at any subsequent visit during pregnancy if not taken at baseline.

*Control participants and participants who have stopped trial CGM intervention only

** Participants in the control arm using continuous glucose monitoring may be asked to share their sensor glucose data with the trial team.

! Trial data: Maternal weight, blood pressure, glucose monitoring method(s), insulin delivery method, diabetes treatment, medication use, hospital admission, episodes of severe hypoglycaemia / hyperosmolar hyperglycaemic state / diabetic ketosis, adverse events.

!! Delivery data: Blood pressure, glucose monitoring method(s), medication use, hospital admission, episodes of severe hypoglycaemia / hyperosmolar hyperglycaemic state / diabetic ketosis, adverse events, pregnancy / diabetes complications, antenatal corticosteroids, method of delivery (vaginal or caesarean), infant birthweight, sex and gestational age, birth injury, length of hospital stay. Intrapartum and inpatient CGM data until maternal hospital discharge.

Infant data: High level neonatal care >24 hours, length of NICU stay, neonatal hypoglycaemia treated with buccal mucosa 40% glucose gel and/or iv dextrose, neonatal hyperbilirubinemia, respiratory distress, length of hospital stay.

6.6.1 Patient visits and assessments

6.6.1.1 Recruitment visit (between confirmed pregnancy and at least 4 days prior to randomisation)

- Checking inclusion and exclusion criteria
- Written informed consent
- Baseline socio-demographic data
- Relevant medical / obstetric history and present medical (diabetes, comorbidity, medication, and obstetric) information
- Body weight and height, calculation of BMI
- Early pregnancy HbA1c recorded (or performed if not previously done in this pregnancy)
- Bloods for metabolic phenotyping (C-peptide, autoantibodies, genetic risk score). If not taken at the recruitment visit, these can be taken at any time during pregnancy.
- Baseline questionnaire pack provided for participants to complete at home (either paper or electronically via link)
- Masked Freestyle Libre sensor insertion (at least 4 days prior to randomisation)

Ideally the sensor will be in place for around 7 days, however if necessary to meet timelines, **at least 4 days of CGM data** should be available prior to randomisation. If there are technical difficulties and/or inadequate CGM data a second CGM sensor may be provided (if possible within the required timeframes). Where only 72-96 hours of data are available, authorisation to randomise should be obtained from Norwich Clinical Trials Unit.

